## 5.2. Exclusion Criteria

Participants are excluded from the study if any of the following criteria apply:

1. Previously participated in a clinical study in which mavacamten was received.
2. Hypersensitivity to any of the components of the mavacamten formulation.
3. Participated in a clinical trial where the participant received any investigational drug (or is currently using an investigational device) within 30 days prior to Screening or 5 times the respective elimination half-life (whichever is longer).
4. Has a prior diagnosis of HCM *OR* a known infiltrative or storage disorder which could cause HFpEF and/or cardiac hypertrophy, such as amyloidosis, Fabry disease, or Noonan syndrome with LV hypertrophy *OR* a positive serum immunofixation result unless a hematologist confirms the patient does not have amyloidosis or multiple myeloma.
5. Has any medical condition that precludes exercise stress testing (for stress echocardiogram).
6. Has a history of syncope within the last 6 months or sustained ventricular tachycardia with exercise within the past 6 months.

CONFIDENTIAL

Approved v2.0

7. Has a history of resuscitated sudden cardiac arrest at any time or known appropriate implantable cardioverter defibrillator discharge within 6 months prior to Screening.
8. Has persistent or permanent atrial fibrillation not on anticoagulation for at least 4 weeks prior to Screening and/or is not adequately rate controlled within 6 months prior to Screening (note: participants with persistent or permanent atrial fibrillation who are anticoagulated and adequately rate-controlled are allowed).
9. For participants on beta blocker, verapamil, or diltiazem, any dose adjustment <14 days before Screening.
10. Currently treated or planned treatment during the study with either: (a) a combination of beta blocker and verapamil or a combination of beta blocker and diltiazem, (b) disopyramide, or (c) biotin or biotin-containing supplements/multivitamins.
11. Has any ECG abnormality considered by the investigator to pose a risk to participant safety (eg, second-degree atrioventricular block type II).
12. Has either: (a) known unrevascularized obstructive coronary artery disease *OR* (b) acute coronary syndrome in the last 3 months.
13. Has known moderate or severe aortic valve stenosis, hemodynamically significant mitral stenosis, or severe mitral or tricuspid regurgitation at Screening (all in the investigator's judgment).
14. Has any acute or serious comorbid condition (eg, major infection or hematologic, renal, metabolic, gastrointestinal, or endocrine dysfunction) that, in the judgment of the investigator, could lead to premature termination of study participation or interfere with the measurement or interpretation of the efficacy and safety assessments in the study.
15. Has severe chronic obstructive pulmonary disease, or other severe pulmonary disease, requiring home oxygen, chronic nebulizer therapy, chronic oral steroid therapy or hospitalized for pulmonary decompensation within 12 months.
16. Hemoglobin < 10.0 g/dL.
17. Body mass index (BMI)  $\geq 45.0 \text{ kg/m}^2$ .
18. Positive serologic test at Screening for infection with human immunodeficiency virus, hepatitis C virus, or hepatitis B virus. Positive hepatitis BsAb participants are allowed as this positive serologic test denotes presence of neutralizing, protective antibodies and does not denote chronic infection.
19. Active COVID-19 infection and/or other acute respiratory infection at time of Screening or randomization.
20. History of clinically significant malignant disease within 5 years of Screening:
  - a. Participants who have been successfully treated for nonmetastatic cutaneous squamous cell or basal cell carcinoma or have been adequately treated for cervical carcinoma in situ can be included in the study.
21. History or evidence of any other clinically significant disorder, condition, or disease (with the exception of those outlined above) that, in the opinion of the investigator or

CONFIDENTIAL

study medical monitor, would pose a risk to participant safety or interfere with the study evaluation, procedures, or completion.

22. Currently taking, or has taken within 14 days prior to Screening, a prohibited medication (including over-the-counter medications) such as CYP2C19 inhibitor (eg, omeprazole, esomeprazole), a strong CYP3A4 inhibitor, or St. John's Wort.
23. Prior or concomitant treatment with cardiotoxic agents such as doxorubicin or similar.
24. Unable to comply with the study requirements, including the number of required visits to the clinical site.
25. Employed by, or a relative of someone employed by MyoKardia, the investigator, or his/her staff or family.
26. Left ventricular global longitudinal strain (GLS) by TTE in the range from 0 to -12.0 (assessed by central TTE reader).
27. Acute decompensated heart failure events requiring intravenous (IV) diuretics, IV inotropes, IV vasodilators, or a left ventricular assist device within 30 days prior to Screening.
28. NT-proBNP at Screening > 2000 pg/mL.
29. Known hypersensitivity or contraindication to the IV echocardiography contrast agent, if contrast echocardiography is required due to inadequate quality of unenhanced echocardiographic images.

### 5.3. Lifestyle Considerations

The following restrictions apply for the specified times during the study period. If a participant does not comply with these restrictions or tests positive in any laboratory tests (eg, drug, alcohol, pregnancy), he/she may be excluded or withdrawn from the study.

- Starting 72 hours prior to the first dose of study drug until the final follow-up visit, participants should not engage in unaccustomed intensive exercise except during protocol-specified exercise tests.
- Starting at Screening, participants will be required to abstain from blood or plasma donation until 3 months after the final study visit.
- Starting on Day 1 until the final follow-up visit, participants will be asked to abstain from grapefruit or grapefruit juice, Seville oranges, and quinine (eg, tonic water).
- Starting at the time of signing informed consent, participants must abstain from taking biotin and biotin-containing supplements/multivitamins.

Contraception requirements are discussed in the inclusion criteria in [Section 5.1](#).

### 5.4. Screen Failures

Screen failures are defined as participants who consent to participate in the clinical study but are not subsequently enrolled in the study. A minimal set of screen failure information is required to ensure transparent reporting of screen failure participants to meet the Consolidated Standards of

Reporting Trials publishing requirements and to respond to queries from regulatory authorities. Minimal information includes demography, screen failure details, eligibility criteria, and any SAE.

Individuals who do not meet the criteria for participation in this study (prescreen or screen failure) may be rescreened.

## 5.5. Criteria for Temporarily Delaying

With consideration to unforeseen circumstances (including those related to the COVID-19 pandemic), randomization and/or initial study drug administration may be delayed, if necessary, upon documented mutual agreement by the study physician and MyoKardia or their designee.

## 6. STUDY DRUG

Study drug is defined as any investigational intervention intended to be administered to a study participant according to the study protocol.

### 6.1. Study Drug Administered

The study drug administered in this study is mavacamten supplied as 2.5 and 5 mg capsules. Mavacamten capsules of both strengths are identical in appearance.

Participants will receive a mavacamten capsule (either 2.5 or 5 mg) once daily for 26 weeks (Day 1 to Week 26).

Study drug will be supplied to participants in 30-count high-density polyethylene bottles that are appropriately labeled. Participants will be instructed to store study drug in a cool, dry place.

Participants will take study drug as directed by the investigator/designee. Participants should be instructed to take study drug at approximately the same time every day. Study drug should be taken with approximately 8 ounces of water. Participants should never take > 1 dose of study drug within an 8-hour period. On study visit days, study drug dosing should be delayed until after study assessments are complete and the study staff instruct the participant to take their daily dose.

Table 2 provides an overview of the study drug.

**Table 2: Study Drug**

Intervention Name	Mavacamten
Type	Drug
Dose Formulation	Capsule
Unit Dose Strength(s)	2.5 mg and 5 mg
Dosage Level(s)	2.5 mg or 5 mg once daily
Route of Administration	Oral
Use	Experimental

**Table 2: Study Drug (Continued)**

Intervention Name	Mavacamten
Investigational Medicinal Product	Mavacamten
Sourcing	Provided by the sponsor
Packaging and Labeling	See Section 6.2

## **6.2. Preparation/Handling/Storage/Accountability**

The investigator or designee must confirm appropriate temperature conditions have been maintained during transit for all study drug received and any discrepancies are reported and resolved before use of the study drug.

Only participants enrolled in the study may receive study drug and only authorized site staff may supply or administer study drug. At the study site and site pharmacy all study drug must be stored in a secure, environmentally controlled, and monitored (manual or automated) area in accordance with the labeled storage conditions with access limited to the investigator and authorized site staff.

The investigator, institution, or the head of the medical institution (where applicable) is responsible for study drug accountability, reconciliation, and record maintenance (ie, receipt, reconciliation, and final disposition records).

Further guidance and information for the final disposition of unused study drug are provided in the Pharmacy Manual.

### **6.2.1. Formulation, Packaging, and Labeling of Study Drug**

Mavacamten capsules are provided as size 2, blue opaque capsules printed with a yellow band on the body and a black band on the cap. Each capsule contains white to off-white powder.

Mavacamten capsules are supplied in 2.5 and 5 mg strengths. Mavacamten capsules of both strengths are identical in appearance.

Mavacamten is manufactured according to current Good Manufacturing Practice regulations. It is supplied in high-density polyethylene bottles with induction seals and child-resistant caps with 30 capsules in each bottle. All bottles are labeled according to applicable local regulatory guidelines.

Mavacamten capsules must be stored at 36°F to 77°F (2°C to 25°C) in the packaging supplied by MyoKardia.

### **6.2.2. Direct-to-Participant Study Drug Shipment (At Selected Sites)**

[figure not shown]
In certain circumstances, it may be necessary to ship study drug directly to a participant to accommodate the participant's schedule through Week 26. Study sites should contact the participant by telephone to confirm study drug delivery. Refer to the Pharmacy Manual for details.

### **6.3. Measures to Minimize Bias: Randomization and Blinding**

This is an open-label study. There will be no blinding at the site level.

### **6.4. Study Drug Compliance**

Participant compliance with study drug dosing will be monitored by capsule count at all study visits from Week 2 through the end of study treatment. Refer to the Pharmacy Manual for details.

### **6.6. Continued Access to Study Drug After the End of the Study**

Not applicable. Currently, there is no continued access to study drug after the end of the study.

### **6.7. Treatment of Overdose**

An overdose is defined as taking more capsules of study drug than directed. An overdose may be suspected by the investigator or spontaneously reported by the participant. An overdose may be symptomatic or asymptomatic. Only symptomatic overdoses should be reported as AEs/adverse events of special interest (AESI).

In the event of symptomatic overdose or in the presence of significant symptoms and/or clinical compromise, the investigator should contact the study medical monitor, and the study drug should be temporarily discontinued. The participant should be closely monitored clinically for AEs/SAEs, with supportive measures undertaken as clinically indicated. If necessary, corrective measures, as described in the 2013 American College of Cardiology Foundation/American Heart Association Guideline for the Management of Heart Failure ([Yancy et al, 2013](#)) and in the 2016 European Society of Cardiology Guidelines for the Diagnosis and Treatment of Acute and Chronic Heart Failure ([Ponikowski et al, 2016](#)), should be implemented. Resumption of study drug must be approved by the study medical monitor.

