Doses of mavacamten used in this study will be 2.5 and 5 mg. Dose adjustments at Week 14 (described in greater detail below) will be based upon NT-proBNP and LVEF measured at the Week 12 visit.

Study visits will occur at Prescreening (optional), Screening, Day 1, Week 6, Week 12, Week 14, Week ■, Week ■, Week 26, and the End of Study (EOS) visit at Week 34. ■

■ Assessments during the treatment period will include vital signs, AEs, concomitant medications, abbreviated physical examination, weight, 12-lead ECG, ■, ■, safety laboratory assessments (chemistry, hematology, coagulation panel, and urinalysis), ■, hs-cTnT, NT-proBNP, urine pregnancy test (for women of childbearing potential only), ■

■

■

■

■. In addition, participants will be contacted via telephone call at Weeks 2, 4, 8, 10, 16, ■, and 24 to collect information about AEs and concomitant medications. Participants who prematurely discontinue study drug at any time will attend an early drug discontinuation visit within 14 days of study drug discontinuation and the EOS visit at Week 34.

CONFIDENTIAL

Approved v2.0

The dose may be [REDACTED] for safety at any time.

Safety will be monitored throughout the study.

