## 3. OBJECTIVES AND ENDPOINTS

Objectives	Endpoints
Primary	

• To evaluate the safety and tolerability of a 26-week course of mavacamten

	

• Frequency and severity of treatment-emergent adverse events (TEAEs), adverse events of special interest (AESIs) [symptomatic overdose, outcomes of pregnancy, left ventricular ejection fraction (LVEF) <math>\leq 30\%</math>], and serious adverse events (SAEs); laboratory abnormalities; vital sign abnormalities; and cardiac rhythm abnormalities

• To evaluate the effect of a 26-week course of mavacamten on N-terminal pro b-type natriuretic peptide (NT-proBNP) levels (at rest)

	

• Change from baseline to Week 26 in NT-proBNP (at rest)

• To evaluate the effect of a 26-week course of mavacamten on cardiac troponin T (cTnT) levels (at rest)

	

• Change from baseline to Week 26 in cTnT (at rest), as assessed by a high-sensitivity assay

CONFIDENTIAL

Approved v2.0

CONFIDENTIAL

Approved v2.0

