### **8.3.6. Adverse Events of Special Interest**

Symptomatic overdose, teratogenicity, and LVEF  $\leq 30\%$  as determined by local site read or centrally read echocardiogram are considered AESIs.

AESIs are required to be reported by the investigator to MyoKardia or their designee within 24 hours, irrespective of regulatory seriousness criteria. If a participant should experience symptomatic overdose, LVEF  $\leq 30\%$ , or if pregnancy outcome becomes known, the investigator will report the information to the study medical monitor and complete the required information in the EDC system within 24 hours of study staff becoming aware of the AESI.

CONFIDENTIAL

Approved v2.0

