#### 9.4.4.1.3. Symptomatic Overdose

The following summaries for reports of symptomatic overdose will be generated, if applicable:

- Number of participants who experienced symptomatic overdose summarized by treatment received
- Analysis of the cause and occurrence of the symptomatic overdose
- TEAE experienced during the symptomatic overdose by primary SOC, HGLT, HLT, and PT showing the number and percent of participants sorted by internationally agreed order of SOC and alphabetic order of HGLT, HLT, and PT

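### Overdose is defined by capsule count although dose varies by capsule strength, so one 5 mg capsule taken for a directed 2.5 mg is twice the dose but not an overdose

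*Combined protocol and SAP*

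**What the plan says.** Section 6.7 gives the only definition of overdose in the visible text: "An overdose is defined as taking more capsules of study drug than directed". It adds that only symptomatic overdoses are to be reported as AEs or AESIs.

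The regimen is in Section 6.1: "Participants will receive a mavacamten capsule (either 2.5 or 5 mg) once daily for 26 weeks". Table 2 gives the same two dose levels. Under Section 4.1 everyone starts on 2.5 mg, and some participants may receive 5 mg from Week 14. Section 6.2.1 says of the capsules: "Mavacamten capsules of both strengths are identical in appearance".

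Three places use the overdose category:

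- Section 3 names it in the primary safety endpoint: "adverse events of special interest (AESIs) [symptomatic overdose, outcomes of pregnancy".
- Section 8.3.6 sets the reporting rule: "AESIs are required to be reported by the investigator to MyoKardia or their designee within 24 hours, irrespective of regulatory seriousness criteria".
- Section 9.4.4.1.3 plans a dedicated summary, which begins: "Number of participants who experienced symptomatic overdose summarized by treatment received".

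Sections 6.7.1, 8.3.6, 9.4.4.1.3, 10.4.1.2 and 10.4.1.4 use the term without redefining it. Section 6.4 monitors compliance by capsule count and refers to the Pharmacy Manual for detail.

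**The concern.** The definition counts capsules, but in this trial the directed number of capsules is always one and only the strength changes. A rule that ignores strength cannot recognise an excess dose that arises from taking the wrong strength. It can also flag a correct total dose made up of two smaller capsules.

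This matters because Section 2.3.1 ties the most likely risks of the drug to higher exposure and an excessive fall in contractility. Symptomatic overdose is one of the few events singled out for expedited reporting and separate tabulation. If a participant has symptoms after a wrong-strength doubling, the written rule drops three things:

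- the AESI classification;
- the 24-hour report, when the event is not an SAE or another AESI;
- the case in the 9.4.4.1.3 summary.

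The error is also hard to notice. The capsules cannot be told apart by eye, and a capsule count that is not kept by strength would look perfect. The biomarker endpoints do not depend on this wording.

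**Working it through.** The plan states no figure on this point, so there is none to reproduce. The check applies the written rule to each way of taking the capsules and compares it with the dose in mg.

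**Inputs**

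- Rule: overdose if capsules taken exceed capsules directed (6.7).
- Directed number: 1 capsule daily at either dose level (6.1).
- Strengths: 2.5 mg and 5 mg (6.1, Table 2).
- Planned size: about 35 participants (9.2). All are assumed to be dosed.

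**Formulas**

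- Dose ratio = (capsules taken × strength taken) / mg directed.
- Extra capsules = capsules taken − 1. The event is classed as an overdose if this exceeds 0.

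**Results**

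| Directed | Taken | Dose ratio | Extra capsules | Rule as written | Rule in mg |
|---|---|---|---|---|---|
| 2.5 mg | 1 × 5 mg | 5 / 2.5 = 2.0 | 1 − 1 = 0 | not an overdose | overdose |
| 2.5 mg | 2 × 2.5 mg | 5 / 2.5 = 2.0 | 2 − 1 = 1 | overdose | overdose |
| 5 mg | 2 × 2.5 mg | 5 / 5 = 1.0 | 2 − 1 = 1 | overdose | not an overdose |

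Rows 1 and 2 deliver the same 5 mg against the same directed 2.5 mg, yet the rule classifies them differently. Row 3 is classed as an overdose with no excess dose. A rule in mg classifies all three by the dose received.

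**Does other text close the gap?** Section 6.1 bars more than one dose within 8 hours. That does not help, because one capsule of the wrong strength is still one dose. The AESI sections repeat the term without a mg threshold. Section 6.7 does not refer to the Pharmacy Manual for the definition.

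**How could row 1 happen?** One route is a dispensing error. Another is 5 mg stock kept after a return to 2.5 mg. The Synopsis (1.1, Study Procedures and Treatment) allows a safety action on dose, but its verb is blacked out: "The dose may be [REDACTED] for safety at any time". The second route is therefore possible but cannot be confirmed from the visible text. Leftover 2.5 mg stock after a move to 5 mg is not a route: substituting one such capsule gives 2.5 / 5 = 0.5 of the directed dose.

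**Size per case.** 1 / 35 = 2.9% of the safety population in the 9.4.4.1.3 count.

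**The case against.** The strongest reply is that the gap is real on paper but small in practice.

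- **The routes are narrow.** No participant should hold 5 mg stock before Week 14. Bottles are labelled, only authorised staff supply drug, and sites reconcile it (6.2, 6.2.1). Section 6.5 is blacked out in the table of contents and the Pharmacy Manual is not available, so controls on dose changes and returned stock may exist that cannot be seen.
- **The dose reached is a study dose.** One 5 mg capsule is the highest dose that this protocol plans, and Section 2.3.1 calls the dosing strategy conservative on that basis.
- **Care of the participant is already covered.** Section 6.7 continues: "In the event of symptomatic overdose or in the presence of significant symptoms and/or clinical compromise, the investigator should contact the study medical monitor". It also requires temporary discontinuation, so significant symptoms trigger action without an overdose label. TEAEs and SAEs are themselves part of the primary safety endpoint, and LVEF ≤30% is a separate AESI.
- **The false positive is harmless.** Two 2.5 mg capsules for a directed 5 mg are reported only if symptomatic, and over-reporting is the cautious direction.
- **A new definition detects nothing.** It classifies an error once it is known. A count by strength relies on the bottle label and would not find a bottle filled with the wrong strength.

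Most of this stands, and it limits the consequence. It does not repair the classification. The benchmark in 6.7 is what the participant was directed to take, and the rule already treats 5 mg as an overdose for a 2.5 mg participant when it comes as two capsules. A participant kept on 2.5 mg may also tolerate 5 mg less well than one selected for it. Some investigators would report a wrong-strength capsule anyway, but about 30 sites would have to depart from the written definition to do so, and they may not all do it.

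**Conclusion.** The concern holds. The definition in 6.7 leaves a doubled dose unclassified when it arises from the wrong strength. It classes the same doubled dose as an overdose when it arises from two capsules, and it also classes a correct 5 mg total taken as two capsules as an overdose. This is a stated rule that gives a wrong classification in a named component of the primary safety endpoint.

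The effect is bounded. A missed symptomatic case loses the AESI label, the 24-hour report if it is not otherwise an SAE or AESI, and one count in 9.4.4.1.3, or 2.9% if all of about 35 participants are dosed. The symptoms remain in the adverse event data. The documents give no rate for wrong-strength errors, and the expected number may be zero. The conclusion assumes that no blacked-out text redefines overdose in mg; no visible text does. The change should be made, but the trial's validity does not turn on it.

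**What to change.** In Section 6.7, replace the capsule-based definition with one in mg, for example: an overdose is a total daily amount of mavacamten, in mg, above the amount directed, whether from extra capsules or from a higher strength than assigned. State that this definition governs the symptomatic-overdose AESI and the 9.4.4.1.3 summary. In Section 6.4, say that capsule counts are kept by strength, unless the Pharmacy Manual already requires this.

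The change is one sentence in 6.7 and, if needed, a few words in 6.4. It adds no visit, sample or participant. It may bring slightly more accountability work and a few more reported overdoses. Amended text needs IRB/IEC approval (10.1.1) across about 30 sites, so it is best included in the next amendment.
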